9.2.1 SUSARs

Procedure for Investigator

Investigator will inform the responsible CRO (who in turn will inform the Sponsor) about the occurrence of the SAE via email within 24 hours of the occurrence of the SAE. The investigator should comply with the local regulatory requirements related to the reporting of unexpected serious adverse drug reactions (SUSARs) to the regulatory authority and IRB.

Study code: NV-05-983-2020
Protocol No.: CVD-04-CD-001
Sponsor name: [name], Limited
Clinical Study Protocol

Procedure for Sponsor

In case of fatal or life threatening unexpected ADRs will be notified to regulatory agencies as soon as possible or no later than 7 calendar days. The follow up report will be submitted within 8 additional calendar days after the first knowledge by the Sponsor that a case qualifies.

In case of serious, unexpected reactions (ADRs) that are not fatal or life-threatening will be filed as soon as possible but no later than 15 calendar days after first knowledge by the Sponsor that the case meets the minimum criteria for expedited reporting.

For unexpected SAE, the Sponsor considers the Investigator's causality assessment but submits an IND safety report to the applicable regulatory authority for those events for which the Sponsor determines there is a reasonable possibility that the drug caused the event (a Suspected Adverse Reaction), regardless of the investigator's causality assessment.

9.3 Exposure *In Utero* During Clinical Studies

If a patient becomes pregnant during the treatment period or within 7 days after the last dose of study treatment, she must not receive additional study drug or treatment and must be promptly discontinued from the study. The patient must be followed up until the outcome of the pregnancy is known (i.e., delivery, elective termination, or spontaneous abortion). If the pregnancy results in the birth of a child, additional follow-up information may be requested.

The Investigator must notify the responsible CRO (at the below mentioned e-mail address) within 24 hours of first learning of the occurrence of pregnancy using the Pregnancy Notification Form providing as much information as possible. The Investigator must notify the responsible CRO about reported complications within 24 hours using the same procedure. Outcome of pregnancy, once known by the Investigator, must also be reported to the responsible CRO within 24 hours using the Pregnancy Outcome Form. Pregnancy communications will be directed to:

Pregnancy Reporting Contact Details Email
--

[contact]
--

CRO who will relay pregnancy notifications to Sponsor. Please note that pregnancy in and of itself is not an AE or SAE. Pregnancy should not be entered into the CRF as an AE unless the Investigator suspects an interaction between the study treatment and contraceptive method. Pregnancy will be documented as the reason for study discontinuation.

CRO will direct the pregnancy communication to Sponsor (Pharmacovigilance and Medical Monitor) as soon as it is received.

9.4 Clinical Laboratory Evaluations

All laboratory values outside the normal range will be evaluated for clinical significance by the Investigator and annotated as clinically significant or not clinically significant. Patients with values

Study code: NV-05-983-2020
 Protocol No.: CVD-04-CD-001
 Sponsor name: [name], Limited
 Clinical Study Protocol

outside of the normal range (at the screening visit) may continue in the study at the Investigator's discretion, provided they do not meet any of the exclusion criteria of the study.

Laboratory tests mentioned in Table 7 will be evaluated at the local laboratory as described in Section 6.3.

When a change in a laboratory test value constitutes an AE, the event should be followed-up until the change resolves or improves even after the end of the study period, within the scope of the patient's cooperation.

Table 7: Clinical / Diagnostic Laboratory Tests

Haematology	Serum chemistry	Urine analysis

 ▪ Haemoglobin ▪ Haematocrit ▪ Total WBC count ▪ Differential WBC count ▪ Platelet count ▪ RBC count ▪ Absolute neutrophil count 	
 ▪ Total Cholesterol ▪ Triglycerides ▪ Total Protein ▪ Albumin ▪ Albumin/Globulin ratio ▪ Blood Urea Nitrogen ▪ Uric acid ▪ Creatinine ▪ Total Bilirubin ▪ Aspartate aminotransferase (AST) ▪ Alanine aminotransferase (ALT) ▪ Gamma-glutamyl transferase ▪ Alkaline phosphatase ▪ Lactate dehydrogenase ▪ Creatine Kinase ▪ Calcium ▪ Phosphate ▪ Sodium ▪ Potassium ▪ Chloride ▪ C-Reactive Protein ▪ Glucose ▪ D-dimer ▪ Ferritin 	
 ▪ Colour ▪ Transparency ▪ pH ▪ Specific gravity ▪ Protein ▪ Glucose ▪ Ketone bodies ▪ Bilirubin ▪ Blood ▪ Nitrite ▪ Urobilinogen ▪ Microscopic examination

Study code: NV-05-983-2020
Protocol No.: CVD-04-CD-001
Sponsor name: [name], Limited
Clinical Study Protocol

9.5 RT-PCR (Qualitative)

Sample collection

The respiratory tract sample will be collected through nasopharyngeal swab or oropharyngeal swab or nasal aspirate or tracheobronchial aspirate (or bronchial lavage at post-baseline assessments) for the RT-PCR (qualitative) assay for SARS-CoV-2 RNA. The sample will be collected at screening, on Day 5, Day 10 and Day 28, or discharge (i.e., if the patient happens to be discharged before one or more of the mentioned timepoints, then the sample will be collected at discharge). No sample will be collected from patients at any timepoint after discharge, EXCEPT if individual patients are scheduled for an additional (unscheduled) visit, either to follow up on an AE or to report a possible 'clinical relapse' of COVID-19 or based on Investigator's discretion during the Day 10 - home visit. A sample will be collected during the unscheduled visit in such cases. The time of sample collection will be recorded.

However, the test may be performed on other days at the Principal Investigator's or a Sub-Investigator's discretion.

Testing of samples

The test will be performed at the site laboratory, if the site laboratory is not capable of performing RT-PCR assay, the testing will be conducted in an approved laboratory.

9.6 Vital Signs

SpO₂, body temperature (axillary), systolic BP, diastolic BP, pulse rate, and respiratory rate will be measured at pre-dose only on Day 1 and at least twice, morning and evening, daily from Day 2 to Day 28 or discharge or discontinuation from the study (whichever is earlier), and the results will be recorded with time of measurement (one measurement of each vital sign is accepted at Study Discontinuation). If more than one measurement is performed in both the morning and evening, the worst value will be recorded. SpO₂ will be measured without oxygen therapy as much as possible. If SpO₂ is measured under oxygen therapy, it should be recorded. If body temperature is ≤ 37.4°C, whether the measurement in question occurred within 4 hours after the use of antipyretic analgesic drugs should be recorded.

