3.1.3.1.2 Safety endpoints

1. Number (and percentage) of patients reporting treatment emergent adverse events (TEAEs) (by MedDRA system organ class and preferred term)
2. Changes of parameters at each assessment during the study/follow-up period, compared to baseline for:
 - Vital signs: body temperature, heart rate, respiratory rate, systolic/diastolic blood pressure (BP) and oxygen saturation.
 - Clinical laboratory assessments: hematology, serum chemistry, urinalysis.
 - 12-lead ECG: Changes in heart rate, PR, QRS, QT and QT_cB intervals.

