6.1.2 Visit 2- Randomization/Baseline Visit [Day 1 (Pre-dose and post-dose)]

The patients who successfully pass the screening tests and meet the eligibility criteria will be enrolled in the study and will be randomized to one of the two treatment groups by IWRS.

The clinical status by WHO 10-point ordinal scale, 8-point ordinal scale, NEWS-2 score and COVID-19 associated symptom severity assessment (i.e., presence or absence, and if present, the severity of individual COVID-19 related symptoms) will be evaluated and recorded. To confirm patient eligibility for randomization (i.e., whether or not [s]he meets inclusion criterion no. 4), the patient's blood oxygen saturation (SpO₂) will be measured once at rest on room air (i.e., without O₂ supplementation). In case of patients with 'severe' (or suspicion of 'severe') COVID-19 disease at baseline, for whom it is not possible to record the SpO₂ on room air, the estimated SpO₂ / FiO₂ ratio (as a surrogate for PaO₂/ FiO₂ ratio) while receiving supplemental oxygen will be used for determining eligibility. Safety assessments (vital signs, partial physical examination, 12-lead ECG will be performed. A chest X-ray will be performed. Pre-treatment AEs will be recorded.

Patients will be administered the study medication as per the treatment group to which (s)he is allocated to by the IWRS system. On Day 1, the second dose will be administered with at least a 4-hour interval from administration of the first dose. Treatment emergent AEs and concomitant medication will be recorded.

The status of each individual patient with respect to admission to the Intensive care unit (ICU) of the hospital (with date of admission), supplemental oxygen (standard or high flow) and mechanical ventilation will be collected.

The investigations (chest X ray and 12 lead ECG) mentioned in Visit 2 - Randomization/Baseline Visit can be waived off if Randomization/Baseline Visit (Visit 2) is being performed on the same day of screening or if the investigations were performed within 72 hours before Randomization/Baseline Visit.

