8.3 Safety Endpoints

Safety endpoint will be as follows:

Stage I

1. Number (and percentage) of patients reporting treatment emergent adverse events (TEAEs) (by MedDRA system organ class and preferred term)
2. Changes of parameters at each assessment during the study/follow-up period, compared to baseline for:
 - Vital signs: body temperature, heart rate, respiratory rate, systolic/diastolic blood pressure (BP) and oxygen saturation.
 - Clinical laboratory assessments: hematology, serum chemistry, urinalysis.
 - 12-lead ECG: Changes in heart rate, PR, QRS, QT and QT_B intervals.

Stage II

1. Number (and percentage) of patients reporting treatment emergent adverse events (TEAEs) (by MedDRA system organ class and preferred term)

9 General Statistical Considerations

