9.3 Definitions

In the following table, the definitions and calculation of derived variables are summarized

Variable / Term	Definition / Way of calculation
Age	Int ((informed consent date – Birth date +1)/365.25)
Baseline	The last valid value prior to the first dose of study treatment
Treatment Start Date	Date of dose administration on Day 1

Statistical Analysis Plan
Sponsor: [name], Inc

Study Number: NV-05-983-2020

Version: 2.0 Date: 06JAN2021

Variable / Term	Definition / Way of calculation
Treatment End Date	Date of Last Study Medication Taken
Duration of exposure	Treatment end date- Date of randomization + 1
Treatment Emergent AE (TEAE)	An AE will be considered as treatment-emergent if the time of onset is on or after the time of the first study drug administration or any AE that exist prior to first dose and its severity increased during the study.
Time to Resolution of Hypoxia	Date of first time the status trial score to become 4 or lower following baseline assessment when evaluated over a period of 24 hours – Date of randomization +1
Time to discharge	Date of discharge – date of randomization + 1
Time to ALL COVID-19 associated symptoms to become '0=absent' or 'mild =1' from Randomization	Earliest Date of ALL COVID-19 associated symptoms to become either '0=absent' or 'mild =1' in assessments over a period of 24 hours – date of randomization + 1
Time to achieve symptom improvement	Date of Change from baseline value for the particular symptom score to become less than or equal to '-1' and sustained at evaluations over a period of 24 hours – Date of randomization +1
Time to Negative	Date of first time to negative conversion in RT-PCR – Date of randomization + 1

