10.7.3 Vital Signs

Vital signs will be measured at Screening, Day 1, Day 2 to Day 28 or discharge (if discharge happens earlier)

Vital signs will be analyzed using SAF population.

The vital signs parameters include:

- Systolic Blood Pressure (mmHg)
- Diastolic Blood Pressure (mmHg)
- Heart Rate (bpm)
- Respiratory Rate (brpm)
- Body Temperature (°F)
- Blood Oxygen Saturation (SpO2) (%)

The actual and change from baseline vital signs parameters will be summarized descriptively by visits and treatment group.

Data listings will be presented for vital signs parameters.

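### The SpO2 safety summary ignores oxygen status at baseline and afterwards, so it mixes room-air and on-oxygen readings and can favour the arm using more oxygen

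*Protocol*

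**What the plan says.** **Endpoint.** Protocol 3.1.3.1.2 includes among the Stage I safety endpoints "Vital signs: body temperature, heart rate, respiratory rate, systolic/diastolic blood pressure (BP) and oxygen saturation". SAP 8.3 repeats it under "Changes of parameters at each assessment during the study/follow-up period, compared to baseline for" the same variables. Protocol 7.2.1 adds that the changes will be compared between the arms.

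**Measurement.** Protocol 9.6 says SpO2 "will be measured without oxygen therapy as much as possible". If SpO2 "is measured under oxygen therapy, it should be recorded". Where more than one measurement is made in a session, "the worst value will be recorded".

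**Baseline.** Day 1 can yield two SpO2 values. Protocol 6.1.2 describes an eligibility reading that "will be measured once at rest on room air", with an exception: severe patients who cannot be read that way are assessed by SpO2/FiO2 while on oxygen. Protocol Table 2 gives this check its own row, apart from the vital-signs row, which also contains SpO2. SAP 9.3 defines baseline as "The last valid value prior to the first dose of study treatment", and Protocol 7.2.1 uses the pre-dose measurement. Neither states an oxygen condition.

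**Analysis.** SAP 10.7.3 lists SpO2 once among the vital signs and says: "The actual and change from baseline vital signs parameters will be summarized descriptively by visits and treatment group". Oxygen status does not appear in that section.

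**The concern.** SpO2 cannot be interpreted without knowing whether the patient was breathing room air or supplemental oxygen. Inclusion criterion 4 means every patient needs oxygen at entry, and many will be weaned during follow-up, so a mix of conditions is the expected state of these data. The protocol asks sites to record the condition, and the SAP then leaves it out of the summary.

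A change from a room-air baseline to an on-oxygen reading contains the effect of the oxygen. A change from an on-oxygen baseline to a room-air reading has the opposite error. If the arms differ in oxygen use, which is close to what the primary endpoint tests, the SpO2 table can flatter the arm whose patients stay on oxygen longer. At stake is the reading of one named respiratory safety summary in a trial about hypoxia.

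**Working it through.** The plan states no SpO2 mean, SD or share of on-oxygen readings, so there is no figure to reproduce. The check sets the rules side by side and then shows the direction of the error with assumed values.

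**Rules taken together**

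- Readings on oxygen are permitted and should be recorded (Protocol 9.6).
- Baseline may be on room air or on oxygen (Protocol 6.1.2, 7.2.1, 9.6; SAP 9.3).
- The summary is split by visit and arm only (SAP 10.7.3).

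No sentence orders the readings to be pooled, but none separates them. A programmer following the plan exactly would pool them.

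**Single patients (all SpO2 values assumed)**

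- Patient A: 90% to 93%, both on room air. Change = 93 − 90 = +3.
- Patient B: 90% on room air at baseline; would now read 88% on room air but is read at 96% on oxygen. Recorded change = 96 − 90 = +6; room-air change = 88 − 90 = −2.
- Patient C: 96% on oxygen at baseline; later weaned and read at 93% on room air. Recorded change = 93 − 96 = −3, although oxygen is no longer needed.

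The patient who worsened shows the largest gain, and the patient who came off oxygen shows a loss.

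**Arm means.** Let u be the rise in SpO2 that oxygen produces (taken as constant), f the share of follow-up readings on oxygen, and b the share of baseline readings on oxygen. Then:

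- observed mean change = room-air mean change + (f − b) × u
- distortion of favipiravir minus placebo = [(f_F − f_P) − (b_F − b_P)] × u

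Randomization makes b_F and b_P equal in expectation, so the between-arm term reduces to (f_F − f_P) × u. With u assumed at 2, 4 or 6 points:

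| f_F vs f_P (assumed) | u = 2 | u = 4 | u = 6 |
|---|---|---|---|
| 20% vs 30% | −0.2 | −0.4 | −0.6 |
| 20% vs 40% | −0.4 | −0.8 | −1.2 |
| 30% vs 60% | −0.6 | −1.2 | −1.8 |
| 40% vs 40% | 0 | 0 | 0 |

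In the last row, if all baselines are on room air (b = 0), each arm's own mean change is still inflated by 0.40 × u = 0.8, 1.6 or 2.4 points. If some baselines are on oxygen, that inflation shrinks and can reverse. The negative signs mean that an arm needing less oxygen looks worse on SpO2 than it should.

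**The case against.** **The table carries little weight alone.** This stands. It is a descriptive summary with no test specified in SAP 10.7.3. Worsening that calls for more oxygen shows elsewhere. The 10-point scale moves from 4 to 5 to 6 with oxygen and then non-invasive ventilation or high flow. NEWS-2 adds 2 points for supplemental oxygen and is analysed by MMRM. ICU care and ventilation are endpoints, and duration of oxygen supplementation is compared by ANOVA (SAP 10.6.2). A reader might infer that respiratory harm would go unseen in this trial. The documents do not support that, because the patient whose SpO2 is held up by oxygen scores worse on these measures.

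**Some context is already planned.** This stands in part. Daily 10-point scores are summarized by visit and arm, and SpO2 is listed. But neither shows under which condition the readings in the SpO2 table were taken.

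**The worst-value rule would usually keep a room-air reading.** True when both kinds are taken in one session. It does nothing when only an on-oxygen reading exists.

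**Baseline may not be on room air.** This stands. The room-air reading is an eligibility check; the pre-dose vital-sign SpO2 falls under the looser rule in Protocol 9.6. A reader might assume a uniform room-air baseline and hence a bias always upward. The text supports neither.

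**Restricting to room-air pairs would do harm of its own.** This also stands. Oxygen status after randomization is an outcome. Such a restriction drops patients with no room-air baseline and everyone still read only on oxygen, and a drug that worsened oxygenation would move its sickest patients out of the table.

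**Conclusion.** The point holds in limited form. Followed as written, SAP 10.7.3 produces an SpO2 safety summary that mixes oxygen conditions both at baseline and at follow-up, and that can favour the arm using more oxygen. The primary endpoint, NEWS-2 and the respiratory-support endpoints are not affected.

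The size cannot be computed from the documents. The 0 to 1.8 points shown rest on assumed uplifts of 2 to 6 points and assumed on-oxygen shares, with a constant uplift and baseline conditions balanced between arms. If oxygen use is equal by arm, there is no between-arm distortion, only arm-level changes that are hard to interpret. A claim that a safety difference will be hidden or reversed goes further than the text allows. What the text supports is that this one table can mislead if read alone, and that the protocol already calls for the information needed to prevent it.

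**What to change.** In SAP 10.7.3:

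1. State which Day 1 SpO2 is the baseline (the eligibility reading or the pre-dose vital-sign reading) and tabulate its oxygen condition by arm.
2. Keep the all-readings summary of actual values and change.
3. Beside it, summarize SpO2 by oxygen status at the reading (room air or on oxygen), with counts and the percentage of patients on oxygen by day and arm.
4. Show change between readings under the same condition only as a supplementary display, labelled as a non-randomized subset. It should not replace the full summary.

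No new visits or measurements are needed. The eCRF is not among the documents, so whether it holds a flag for each reading is unknown. If it does not, the oxygen details collected daily under Protocol 6.1.3 can be used, at the price of day-level rather than reading-level status. The cost is a somewhat larger table, and subsets defined after randomization that must be read together with the percentage on oxygen.

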9.7 Electrocardiograms

12-lead electrocardiogram (ECG) will be recorded with the patient at rest in the supine position at screening, once daily (preferably at the same time on each day) on Day 1, Day 4, Day 7, Day 10, Day 14, Day 21 and Day 28 or discharge (if discharge happens earlier than one or more of the above-mentioned assessment timepoints) or Study Discontinuation, whichever is earlier, and heart rate (HR), RR, PR, QRS, QT and QTcB intervals, and the presence or absence of clinically significant abnormalities will be recorded. Changes in ECG parameters will be recorded as AEs if the Investigator judges these as being clinically significant.

Study code: NV-05-983-2020
Protocol No.: CVD-04-CD-001
Sponsor name: [name], Limited
Clinical Study Protocol

9.8 Physical Examination Findings

The Physical Examination will be performed, and results will be documented at visits as described in [Section 6.3](#). Changes to physical examination from screening to end of trial will be recorded as AEs if the Investigator judges these as being clinically significant.

A complete physical examination includes general appearance, skin, head, neck, ENT, heart, lungs, abdomen, extremities, neurological, musculoskeletal, and lymph nodes.

A partial physical examination includes general appearance, ENT, heart, lungs and lymph nodes.

9.9 Other Safety Assessments

Serum pregnancy test will be conducted in case of women of childbearing potential at screening and End of Study (Day 28 or discharge, whichever is earlier).

10 OTHER ASSESSMENTS

Not applicable.

Study code: NV-05-983-2020
Protocol No.: CVD-04-CD-001
Sponsor name: [name], Limited
Clinical Study Protocol

11 STATISTICAL METHODS

11.1 Analysis Sets

Four Analysis populations will be considered for this study which are defined as below.

Screened Population: All participants who signed the informed consent form.

Safety Population (SAF): All randomized patients who received at least one dose of the study medication.

Intention-to-treat (ITT): All randomized patients who received at least one dose of the study medication.

Modified Intention to treat (mITT): All randomized patients who received at least one dose of the study medication and has at least one post dose primary efficacy endpoint assessment available.

(Note: If there is a greater than 5% difference in the number of patients in the ITT and mITT populations, then analyses for mITT population will be provided additionally)

Per protocol set (PPS): All patients included in the ITT who complete the study without major protocol deviation which would affect the primary endpoint of the study.

11.2 General Statistical Considerations

Adverse events and medical history will be classified using standard Medical Dictionary for Regulatory Activities (MedDRA Version 23.0) terminology. Prior and concomitant medications (including medications which are a part of supportive care) will be coded with the World Health Organization Drug Global (WHO-DG, version March 1, 2020) dictionary as applicable.

Unless otherwise specified, the primary efficacy analysis will be done using ITT population. The statistical significance level is 0.05 by one sided or two-sided test, wherever appropriate. Mean/Median estimate (and other general statistics such as Inter quartile range, SD, min, max) and the 95% CI for the estimates of the mean will be provided for the applicable efficacy endpoint. Endpoints will be analysed descriptively and inferentially wherever necessary. Details of the statistical methods will be described in the SAP, which will be finalized before study database lock of Stage I of the study.

Description of statistics:

The primary indicators collected in this study will be described by appropriate statistical methods. To briefly mention, Quantitative indicators will be described by arithmetic mean, standard deviation, median, inter quartile range, maximum, minimum etc.; qualitative indicators will be described by frequency and percentage.

